### 8.3.3.3 EXPECTEDNESS

A clinician with appropriate expertise in nephrology/dialysis will be responsible for determining whether an adverse event (AE) is expected or unexpected. An AE will be considered unexpected if the nature, severity, or frequency of the event is not consistent with the risk information previously described for the study procedures. As described previously some discomfort to mentors during training and their mentoring activities is expected. Some conflicts may also arise between the mentor/mentee pairs which are to be expected as well. These occurrences will be considered "expected".

The following serious adverse events are anticipated in the hemodialysis population and are not considered "unexpected" or Unanticipated Problems. Note that the designation as "Anticipated" does not imply that the event is not an SAE but relates to the regulatory definition of Unanticipated Problems as provided in Section 8.4.

- Death
- Coronary Ischemia including:
  - Unstable angina
  - Acute MI
  - Coronary revascularization
- Heart failure hospitalization or exacerbation
- Cardiac arrest
- Cardiac arrhythmia (ventricular or atrial)
- Peripheral vascular revascularization
- Amputation
- Hypotension
- Hypertension
- Nausea or vomiting
- Vascular Access Events including:
  - Catheter exchange, removal or thrombolysis
  - Arteriovenous graft or fistula complications

- Thrombosis
- Stenosis
- Revascularization
- Infection
- Infections including:
  - Pneumonia
  - Bacteremia
  - Hemodialysis vascular access infection

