#### 8.3.5 ADVERSE EVENT REPORTING

All AEs will be assessed by a principal investigator, using the above protocol defined grading system. Disease-related events common in the study population are described in 8.3.3.3. All AEs will be documented on the AE Study Log Form and also in the individual participant research record. If the AE meets the criteria for an SAE it will be documented accordingly and reported to the PIs, DSMB and IRB if indicated (Unexpected and Probably or Definitely related to the Intervention). Events that meet criteria for reporting to the IRB, this will occur within 10 business days and also summarized in the continuing review. If the event is unexpected probably or related to the intervention and results in death, the event will be reported to the IRB within 3 days and also summarized at the continuing review, or as required by the local IRB.

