### 8.4.2 UNANTICIPATED PROBLEMS REPORTING

The investigator will report unanticipated problems (UPs) to the reviewing Institutional Review Board (IRB) and to the DSMB and lead PI. The UP report will include the following information:

- Protocol identifying information: protocol title and number, PI's name, and the IRB project number
- A detailed description of the event, incident, experience, or outcome
- An explanation of the basis for determining that the event, incident, experience, or outcome represents an UP
- A description of any changes to the protocol or other corrective actions that have been taken or are proposed in response to the UP

To satisfy the requirement for prompt reporting, UPs will be reported using the following timeline:

- UPs that are serious adverse events (SAEs) will be reported to the IRB and to the DCC/study sponsor/funding agency within 10 days of the investigator becoming aware of the event. However,

- if the UP is classified as probably or related to the intervention and results in death the IRB will be notified within 3 calendar days, or as required by the local IRB.
- If the unanticipated problem is unrelated to the intervention it will be documented on the Adverse Event Study Log Form and summarized and reported to the DSMB as part of continuing review.

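### Section 8.3.3.3 lists death and other events as not unexpected whatever their relatedness, which contradicts the expedited IRB reports in 8.3.5 and 8.4.2

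*Combined protocol and SAP*

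**What the plan says.** **8.3.3.3, first paragraph.** A clinician decides expectedness by a general test, whose yardstick is the risks of what the study itself does: "An AE will be considered unexpected if the nature, severity, or frequency of the event is not consistent with the risk information previously described".

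**8.3.3.3, list.** A second paragraph introduces a fixed list: "The following serious adverse events are anticipated in the hemodialysis population and are not considered" unexpected or UPs. Death is the first entry. Acute MI, cardiac arrest, arrhythmia, hypotension, pneumonia and bacteremia are among the others. No entry is limited by cause or by relatedness. The section adds that a listed event may still be an SAE, and that the designation "relates to the regulatory definition of Unanticipated Problems as provided in Section 8.4".

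**8.3.5 (applied to SAEs by 8.3.6).** An SAE goes to the IRB if it is "Unexpected and Probably or Definitely related to the Intervention", within 10 business days. The shorter clock has its own condition, "unexpected probably or related to the intervention and results in death, the event will be reported to the IRB within 3 days", with room for what the local IRB requires.

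**8.4.1 and 8.4.2.** A UP must meet three criteria, and the first is that it is unexpected. Under 8.4.2, "if the UP is classified as probably or related to the intervention and results in death the IRB will be notified within 3 calendar days", again subject to local IRB requirements.

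**The concern.** The rules in 8.3.5 and 8.4.2 assume that some deaths related to the intervention will be unexpected, since otherwise there would be nothing to report within 3 days. The list in 8.3.3.3 says that death is not unexpected and not a UP, and it makes no exception for a death that the investigator attributes to the study. A site that follows the list and a site that follows the general test one paragraph above it could handle the same death differently: one would notify the IRB within 3 days, and the other would have no deadline shorter than the six-monthly case reports. What is at stake is prompt IRB notice of a death judged to be caused by the study, while other mentor/mentee pairs are still in their 3-month intervention.

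**Working it through.** No arithmetic applies; the plan gives no figure to reproduce. The check is to trace the conditions.

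**Conditions**
- 10-business-day report (8.3.5): unexpected AND probably or definitely related.
- 3-day report (8.3.5): unexpected AND related AND results in death.
- 3-calendar-day report (8.4.2): UP AND related AND results in death. By 8.4.1, a UP must itself be unexpected.

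The two fatal-event rules give the relatedness level in slightly garbled form. I read it as probably or definitely related, in line with the main condition in 8.3.5.

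**Result for a death judged probably or definitely related**

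| What is classified | Rule applied in 8.3.3.3 | Unexpected? | 10-business-day | 3-day (8.3.5) | 3-calendar-day (8.4.2) |
|---|---|---|---|---|---|
| Death itself | List | No | Blocked | Blocked | Blocked |
| A listed event with fatal outcome (acute MI, cardiac arrest, bacteremia) | List | No | Blocked | Blocked | Blocked |
| Death itself | General test | Can be yes | Can apply | Can apply | Can apply, if the other UP criteria are met |
| An event not on the list, with fatal outcome | General test | Can be yes | Can apply | Can apply | Can apply, if the other UP criteria are met |

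Rows 1 and 3 are the same death under two paragraphs of one section, with opposite results. Section 2.3.1 does not name death caused by the study procedures as a risk; a pair member's death appears there only as a source of distress. The general test therefore points to unexpected where the list says the reverse.

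**What is left when the list blocks the reports**
- 8.3.3.1 sends severe, related events to the IRB and DSMB with no expectedness condition, but sets no deadline. Severe is also not one of the four grades on its own scale (not serious, serious, life-threatening, fatal).
- 7.1 has safety concerns within a pair recorded as an AE and reported to the DSMB, and a summary of events sent to the IRB. It sets no deadline.
- 10.1.6 sends case reports to the DSMB and IRB at least every six months, which is twice the 3-month intervention.

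**Is the unqualified entry needed to keep ordinary dialysis deaths out of expedited reporting?** No. The relatedness condition in 8.3.5 and 8.4.1 already excludes them, and 8.4.1 already judges expectedness in light of the population studied. For these reports, the unqualified entry changes the outcome only for deaths that pass the relatedness condition.

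**The case against.** **Death is an outcome, not the event.** Both fatal-event rules concern an event or UP that results in death. If the underlying event is what is classified, a fatal event outside the list can be unexpected and related, and both rules work. This stands, and it limits the point. A reader might infer that no death could ever reach a 3-day report, or that suicide and violence between a pair are the very events excluded. The documents do not support either inference: neither suicide nor violence is on the list. The objection does not remove the conflict, because 8.3.3.3 names death itself as an event, the protocol never chooses between the two ways of classifying, and listed events with a fatal outcome stay blocked either way.

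**Pair conflicts.** The same section says "Some conflicts may also arise between the mentor/mentee pairs which are to be expected as well". A reader might infer that a serious assault is therefore expected. That does not follow, since severity is part of the general test.

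**The list is scoped to disease.** It is introduced as what is anticipated in hemodialysis patients, 8.3.5 describes its contents as disease-related, and a clinician makes the determination. This is probably the intention, but the entries do not say so, and the designation is expressly tied to the UP definition.

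**Other routes exist.** It would be wrong to infer that related deaths never reach the IRB: 7.1, 8.3.3.1 and 10.1.6 provide for it, the DSMB can meet as needed, 7.1 withdraws participants from the intervention over safety concerns, and local IRB rules may be stricter. None of these restores a short deadline within the protocol itself.

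**Minimal risk.** Section 8.3.1 rates the study as no more than minimal risk, so related deaths should be rare. That lowers the expected number of affected reports but does not reconcile the text.

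**Conclusion.** The contradiction is real, in a limited form. Read literally, the unqualified list in 8.3.3.3 disables both 3-day IRB reports and the 10-business-day report for a death judged probably or definitely related to the intervention, whenever death or another listed event is what is classified. It also contradicts the general test in the same section. Events off the list with a fatal outcome are not affected.

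The size is a matter of timing. For such a death, 3 days becomes either no stated deadline or up to six months, unless the local IRB requires more. How many deaths would be affected cannot be derived: the documents give no mortality figure, and all-cause deaths would not measure it, because only those judged related count. No endpoint or analysis is touched. The conclusion rests on reading the list as written and on the relatedness reading stated in the working.

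**What to change.** Reconcile 8.3.3.1, 8.3.3.3, 8.3.5, 8.4.1 and 8.4.2. In 8.3.3.3, state that:

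1. the anticipated list covers only events attributed to the underlying disease and not judged related to the study; and
2. any death or listed event judged probably or definitely related is assessed for expectedness case by case against the study's own risk information.

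The existing 3-day rules can then apply without being rewritten. Relatedness decides only whether the list may be used as a shortcut; expectedness remains a separate clinical judgement, as 8.3.3.2 and 8.3.3.3 intend. The change does not bring deaths graded only potentially related under the 3-day rules, which still require a higher grade. Whether it should is for the sponsor and the IRB to decide.

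The cost is a wording amendment and at most a few more expedited reports, since ordinary disease-related deaths stay excluded by the relatedness condition.

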#### 8.3.4 TIME PERIOD AND FREQUENCY FOR EVENT ASSESSMENT AND FOLLOW-UP

The occurrence of an adverse event (AE) may come to the attention of study personnel during study visits and interviews of a study participant presenting for medical care, or review by a study monitor. All AEs, not otherwise precluded per the protocol, will be captured on the Adverse Event Log Form. Information collected includes event description, time of onset, clinician's assessment of severity, relationship to study procedures (assessed only by those with the training and authority to make a diagnosis), assessment of expectedness, and time of resolution/stabilization of the event. All AEs will be followed to adequate resolution.

Any medical or psychiatric condition that is present at the time that the participant is screened will be considered as baseline and not reported as an AE. Changes in the severity of an AE will be documented to allow an assessment of the duration of the event at each level of severity to be performed. Documentation of onset and duration of each episode will be maintained for intermittent AEs.

In this study, ED visits and hospitalizations, including reasons for these encounters, are collected as solicited events as they serve as the primary outcome. Vascular access use are solicited, and satisfaction with the intervention will be solicited monthly.

The study PIs, with the help of the research assistants, will record adverse events with start dates occurring any time after informed consent is obtained until 7 (for non-serious AEs) or 30 days (for SAEs) after the last day of study participation. At each study visit, the investigator will inquire about the occurrence of AE/SAEs since the last visit. Events will be followed for outcome information until resolution or stabilization.

#### 8.3.5 ADVERSE EVENT REPORTING

All AEs will be assessed by a principal investigator, using the above protocol defined grading system. Disease-related events common in the study population are described in 8.3.3.3. All AEs will be documented on the AE Study Log Form and also in the individual participant research record. If the AE meets the criteria for an SAE it will be documented accordingly and reported to the PIs, DSMB and IRB if indicated (Unexpected and Probably or Definitely related to the Intervention). Events that meet criteria for reporting to the IRB, this will occur within 10 business days and also summarized in the continuing review. If the event is unexpected probably or related to the intervention and results in death, the event will be reported to the IRB within 3 days and also summarized at the continuing review, or as required by the local IRB.

#### 8.3.6 SERIOUS ADVERSE EVENT REPORTING

SAEs will be evaluated as described previously and recorded on the Adverse Event Study Log Form. This include information about if the study intervention was discontinued, the reason why the event is classified as serious, and the assessment of relatedness to the intervention. Any additional records for evaluation will be requested as needed and continue until the event is resolved. AE forms may be completed by research coordinators, but must be reviewed and signed by a site investigator. SAEs that

are ongoing at the end of the trial will be followed to determine the final outcome. SAEs will be reported as per the timeline and requirements for AEs (Section 8.3.5).

### 8.3.7 REPORTING EVENTS TO PARTICIPANTS

Study findings, including an aggregated report about AEs and SAEs will be available to study participants in publicly available online sources (clinicaltrials.gov), scientific literature and any associated reports, and potentially websites of the investigators, or their organizations.

### 8.3.8 EVENTS OF SPECIAL INTEREST

N/A

### 8.3.9 REPORTING OF PREGNANCY

N/A

## 8.4 UNANTICIPATED PROBLEMS

### 8.4.1 DEFINITION OF UNANTICIPATED PROBLEMS

This protocol uses the definition of Unanticipated Problems as defined by the Office for Human Research Protections (OHRP). OHRP considers unanticipated problems involving risks to participants or others to include, in general, any incident, experience, or outcome that meets all of the following criteria:

- Unexpected in terms of nature, severity, or frequency given (a) the research procedures that are described in the protocol-related documents, such as the Institutional Review Board (IRB)-approved research protocol and informed consent document; and (b) the characteristics of the participant population being studied;
- Related or possibly related to participation in the research (“possibly related” means there is a reasonable possibility that the incident, experience, or outcome may have been caused by the procedures involved in the research); and
- Suggests that the research places participants or others at a greater risk of harm (including physical, psychological, economic, or social harm) than was previously known or recognized.

Examples may include events such as loss of study equipment with private information, or complaints by participants, family or staff members.

### 8.4.2 UNANTICIPATED PROBLEMS REPORTING

The investigator will report unanticipated problems (UPs) to the reviewing Institutional Review Board (IRB) and to the DSMB and lead PI. The UP report will include the following information:

- Protocol identifying information: protocol title and number, PI's name, and the IRB project number
- A detailed description of the event, incident, experience, or outcome
- An explanation of the basis for determining that the event, incident, experience, or outcome represents an UP
- A description of any changes to the protocol or other corrective actions that have been taken or are proposed in response to the UP

To satisfy the requirement for prompt reporting, UPs will be reported using the following timeline:

- UPs that are serious adverse events (SAEs) will be reported to the IRB and to the DCC/study sponsor/funding agency within 10 days of the investigator becoming aware of the event. However,

- if the UP is classified as probably or related to the intervention and results in death the IRB will be notified within 3 calendar days, or as required by the local IRB.
- If the unanticipated problem is unrelated to the intervention it will be documented on the Adverse Event Study Log Form and summarized and reported to the DSMB as part of continuing review.

#### 8.4.3 REPORTING UNANTICIPATED PROBLEMS TO PARTICIPANTS

Reporting of UPs to participants will depend on the nature of the UP. This may include:

- Modification of informed consent documents to include a description of newly recognized risks
- Provision of additional information about newly recognized risks to previously consented/enrolled participants.

### 9 STATISTICAL CONSIDERATIONS

#### 9.1 STATISTICAL HYPOTHESES

- Primary Endpoint:  
The primary objective is to determine the effectiveness of a peer support telephone intervention compared with usual care to reduce a composite of ED visits and hospitalizations among patients receiving in-center hemodialysis for ESKD. The null hypothesis is that the count of composite events at the end of the study period between intervention and usual care are the same. The alternative hypothesis is that the count of composite events at the end of the study period are different.
- Secondary Endpoint(s):
  - To determine the effectiveness of a peer support phone intervention compared to usual care to improve:
    - dialysis self-management including:
      - Dialysis treatment schedule adherence (mean minutes missed per month)
      - Inter-dialytic weight gain (IDWG) (mean monthly %)
    - nutritional status (serum albumin)
    - dialysis knowledge
    - dialysis self-management self-efficacy
    - social support (general and dialysis-specific)
    - coping skills
    - quality of life
    - communication with providers
- The null hypothesis is that the secondary endpoint values at the end of the study period between intervention and usual care are the same. The alternative hypothesis is that the secondary endpoint values at the end of the study period are different.
- Feasibility endpoint(s):
  - To determine the feasibility of a structured, multicomponent, multiple session peer mentor training program at two sites. There is no specified hypothesis.
  - To determine the acceptance of peer mentor phone intervention by patients. There is no specified hypothesis.

**Table 4. Scientific Questions to be Addressed with the Trial**

Scientific question	Outcome(s)	Analysis
1. Does phone peer support improve outcomes at 18-months (*12 to 18-months)?	
 
Primary: composite endpoint count of ED visit and hospitalization events
 
Secondary: Various as listed above
 
	Poisson regression with two random intercepts. Random intercepts account for clusters by (1) mentor; (2) dialysis unit  See Section 9.4.2 (Primary); 9.4.3 (Secondary)
2. Is a peer mentor training program feasible?	
 
Attendance records
 
Pre- and Post-knowledge test scores
 
Satisfaction with training
 
Summative assessment
 
	Paired t-tests  Descriptive summaries and content analysis of qualitative data
3. Is a peer mentor training program accepted by patient receiving hemodialysis	
 
Satisfaction with intervention
 
Communication rating of mentors
 
	Descriptive  Content analysis of qualitative data

## 9.2 SAMPLE SIZE DETERMINATION

For evaluation of the primary endpoint, estimates are based on local dialysis unit hospitalization events in the past 12 months. For the control group, we expect 0.27 events per month (100 prevalent patients and 27 composite events per month). With 73 patients per group (after 25% drop-out), our study has >80% power to detect 20% reduction (i.e. a reduction of 0.054 visits per person-month) at type 1 error level 0.05. We will recruit at least 100 patients per group over the course of the study.

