## 1 PROTOCOL SUMMARY

### 1.1 SYNOPSIS

**Title:** Peer Mentorship to improve outcomes in patients on maintenance hemodialysis

**Short Title:** PEER-HD

**Grant Number:** R18DK118471

**Study Description:** Pragmatic trial to test the effects and implementation of a low cost, educational, telephone-based, peer-mentor intervention on ED visits and hospitalizations among high-risk patients receiving hemodialysis.

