## 5.1 INCLUSION CRITERIA

### Mentors

Mentor participants must meet all of the following inclusion criteria:

1. Provision of signed and dated informed consent form
2. Stated willingness to comply with all study procedures and availability for the duration of the study
3. Males and females; Age > 21 years
4. Diagnosis of ESKD and treatment with in-center hemodialysis for at least 1 year at the time of recruitment
5. Dialysis treatment at one of the participating dialysis units
6. No hospitalizations in the prior 6 months
7. No unexcused absence or shortening (2 or more x 10 minutes per treatment) of dialysis treatments in the past 6 months
8. Use of an AV fistula or graft as dialysis access
9. Serum albumin 3.5 g/dL or greater in the month prior to enrollment
10. Fluent in English (or Spanish – Bronx, NY site)

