### Patient Participants [Intervention or Usual Care]

Patient participants must meet all of the following inclusion criteria:

1. Provision of signed and dated informed consent form
2. Stated willingness to comply with all study procedures, including randomization, and availability for the duration of the study
3. Males and females; Age > 21 years
4. Dialysis treatment at one of the participating dialysis units
5. One of the following criteria:

- a. Diagnosis of ESKD and treatment with in-center hemodialysis for less than 90 days
- b. One or more hospitalizations in the prior month
- c. One or more ED visits in the prior month
- d. More than 1 unexcused missed dialysis treatments in the prior month
- e. 2 or more shortened (more than 10 minutes) dialysis treatments in the prior month
- f. Use of a catheter for dialysis access
- g. An average of more than 4% IDWG in any week during the prior month
- h. Serum albumin less than 3.5 mg/dL in the prior month
6. Fluent in English (or Spanish – Bronx, NY site)

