## 9.3 POPULATIONS FOR ANALYSES

For the primary endpoint comparison, an intention-to-treat analysis will be used, including all available data on randomized participants. It is expected that up to 20% of randomized participants may discontinue from the study prior to the end point. These participants will be included in the primary analysis and data from the monthly outcome ascertainment up until the last available time point will be used. As preparation for the follow-up period modification, events to date were evaluated at one site (Einstein) and were found to be more frequent than initial estimates. This informed the request for reduction in the follow-up period.

The characteristics of those who do not complete all study activities will be compared to those with complete follow-up to examine for potential biases introduced by differential follow-up among the two groups. These will be considered ancillary analyses.

Secondary analyses will examine additionally an as-treated population. This will group any intervention patient who did not participate in more than 20 minutes total of the intervention during the three-month period to be classified as the usual care group.

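### Section 9.2 still sizes the trial on 0.27 events per month from prevalent unit patients, and the plan does not show that the higher rate it reports offsets the shorter follow-up

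*Combined protocol and SAP*

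**What the plan says.** Section 9.2 says that "estimates are based on local dialysis unit hospitalization events in the past 12 months", and then: "For the control group, we expect 0.27 events per month (100 prevalent patients and 27 composite events per month". It mentions no restriction to patients who would be eligible. On that rate, with 73 per group after 25% drop-out, it claims more than 80% "power to detect 20% reduction (i.e. a reduction of 0.054 visits per person-month) at type 1 error level 0.05". It plans to recruit at least 100 per group and states no follow-up time.

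The Synopsis describes the target as "ED visits and hospitalizations among high-risk patients receiving hemodialysis". Section 5.1 requires patient participants in either arm to meet one of eight criteria. One is "One or more hospitalizations in the prior month"; the others include a recent ED visit, catheter use, missed or shortened sessions, low albumin and under 90 days on dialysis. Mentors come from the opposite end of the same units, with "No hospitalizations in the prior 6 months" among their criteria.

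Sections 1.1 and 1.2 cut observation from 18 months to 12, or to between 12 and 18 months for those already further along. Section 9.3 gives the supporting evidence: "events to date were evaluated at one site (Einstein) and were found to be more frequent than initial estimates". It reports no rate, no person-time and no arm.

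**The concern.** Two things in Section 9.2 do not match the trial as amended. First, the rate describes prevalent patients in a unit, while the trial enrols patients selected for risk; two of the eight criteria are recent occurrences of the primary endpoint itself. Second, the plan relied on a higher observed rate to shorten follow-up, but did not carry that rate into the sizing.

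What is at stake is whether the shorter follow-up can be justified from the document. Information for a rate comparison depends on events, that is, on rate times person-time. Person-time was cut, and the compensating rise in the rate is asserted without a number. The absolute target is affected too, since 0.054 equals 20% only when the control rate is 0.27.

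**Working it through.** **Inputs.** From 9.2: control rate r = 0.27 per person-month, 20% reduction (rate ratio 0.80), 73 per group, alpha 0.05. From 9.4.1: two-sided tests. From 1.1 and 1.2: 18 months originally, 12 months (12 to 18 for some) as amended. From 9.3: up to 20% may discontinue, with their data kept to the last available time point. From 9.4.2: log follow-up time as offset.

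**Formula.** For person-months P per group under a plain Poisson model:

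power = Φ( |ln 0.80| / √(1/(P·r) + 1/(P·0.80·r)) − 1.960 ), with |ln 0.80| = 0.2231.

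**1. The plan's own figure.** P = 73 × 18 = 1,314 and r = 0.27. The standard error is 0.0796, and 0.2231/0.0796 − 1.960 = 0.842, giving 80.0%. The smallest n per group reaching 80% is 73, and 73/0.75 rounds up to 98, consistent with recruiting 100. So 9.2 is arithmetically right for 0.27 over 18 months.

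**2. Shorter follow-up, same rate.**
- P = 73 × 12 = 876: standard error 0.0975, power 62.9%.
- P = 75 × 12 + 25 × 6 = 1,050 (100 recruited, 25% discontinuing with an assumed mean of 6 months): standard error 0.0891, power 70.7%.
- P = 80 × 12 + 20 × 6 = 1,080 (20% discontinuing, same assumption): standard error 0.0878, power 71.9%.

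**3. Effect of a higher control rate, 20% reduction held.** The documents give no rate for eligible patients, so these rates are assumed.

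| Control rate | 20% as absolute | 1,314 (9.2 as sized) | 876 | 1,050 | 1,080 |
|---|---|---|---|---|---|
| 0.27 | 0.054 | 80.0% | 62.9% | 70.7% | 71.9% |
| 0.30 | 0.060 | 84.0% | 67.4% | 75.2% | 76.4% |
| 0.35 | 0.070 | 89.1% | 74.0% | 81.4% | 82.4% |
| 0.40 | 0.080 | 92.7% | 79.5% | 86.2% | 87.1% |
| 0.50 | 0.100 | 96.8% | 87.6% | 92.6% | 93.3% |

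In every column a higher rate raises power.

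**4. Rate needed for 80%.** Expected control events needed = (1.960 + 0.842)² × (1 + 1/0.80) / 0.2231² ≈ 355. Dividing by person-months: 355/876 ≈ 0.405, 355/1,050 ≈ 0.34, 355/1,080 ≈ 0.33. These are 1.5, about 1.25 and about 1.2 times 0.27.

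**5. What is left out.** Section 9.4.2 specifies random intercepts for mentor and facility, with a quasi-Poisson fallback; the sizing has no allowance for either. As an illustration, an assumed variance inflation of 2 takes the original 80.0% (0.27, 1,314 person-months) to about 51%.

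**The case against.** The strongest reply is that sizing on a lower-risk population is safe. Section 9.2 states the target as a 20% reduction and derives 0.054 from it. With that held, a rate above 0.27 gives more power (89.1% at 0.35 over 18 months). This stands: the source of the rate does not by itself make the trial too small, and the fall to 63% comes wholly from cutting 18 months to 12.

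It is also fair that 73 × 12 understates the person-time. Section 9.3 keeps discontinuers' data, and some participants have between 12 and 18 months. This stands too. It is why the required rate is a range, and time beyond month 12, whose amount the plan does not give, would lower it further.

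The gap between populations may also be modest. Eligibility needs only one of eight broad criteria, and Section 2.2.3 cites 34% of patients skipping treatments and up to 20% of prevalent patients using catheters. Section 9.2 does not say that its 100 patients were the whole unit; that is a natural reading, not a stated fact. A modest gap would not rescue the plan, however, because the rate would then lie close to 0.27, where the shorter follow-up is not offset.

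Finally, the DSMB and the NIH program officer approved the change (Section 1.2). That settles its authorisation, but leaves Section 9.2 out of date.

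**Conclusion.** The point holds as one about stale and unsupported sizing figures. By the plan's own account events were more frequent than first estimated, yet 9.2 keeps 0.27, 0.054 and power above 80%. That power belongs to 0.27 with 1,314 person-months per group. With amended follow-up at 0.27 it is about 63% to 72%, and 80% needs a control rate of roughly 0.33 to 0.405. These figures assume plain Poisson counts, a 20% relative reduction, a mean of 6 months for discontinuers in the upper person-time cases, and no time beyond month 12.

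A reader might infer three stronger things that the documents do not support:
- **That the wrong-population rate leaves the trial underpowered.** At a fixed 20% reduction the bias runs the other way.
- **That 0.405 is the rate the trial must reach.** It applies only to exactly 876 person-months per group.
- **That Section 9.3 establishes how far the control rate exceeds 0.27.** It covers one site, gives no value and names no arm, so the size of the mismatch is unknown. A rise to 0.30 would not offset the cut in any 12-month case above; a rise to 0.50 would in all of them.

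**What to change.** - **Section 9.2, rate:** replace 0.27 with the observed event rate per person-month in enrolled participants, pooled over arms and over both sites, with the person-months behind it. Pooling shows no treatment comparison. Under a 20% reduction with equal person-time the pooled rate is (1 + 0.80)/2 = 0.9 of the control rate, so the implied control rate is the pooled rate divided by 0.9.
- **Section 9.2, target:** state it as a 20% relative reduction, with the absolute value matching the revised control rate.
- **Section 9.2, power:** restate it from the expected total person-months under 12 to 18 months of follow-up, counting discontinuers' time, and say what is assumed about overdispersion and about mentor and facility clustering. Do not print 0.405 as a fixed threshold.
- **Section 9.3:** give the rate behind the one-site statement and the corresponding rate for the Nashville site.

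The cost is one pooled tabulation of monthly outcome data already collected and a rewritten sizing paragraph. Recruitment, endpoint and analysis need not change. The downside is that the restated power may fall below 80%.
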